#### **3.1.1 Baseline and Change from Baseline**

For all assessments recorded in this study, baseline is defined as the last non-missing value prior to the first dose of study medication (scheduled or unscheduled).

Any assessments taken on the same day of first dose will be deemed to have been collected pre-dose and therefore eligible to be selected as the baseline value. If measurement from Visit 2 is missing, Visit 1 or other unscheduled visit will be used.

Change from baseline will be calculated as difference between the values measured at a specific time point after baseline minus baseline value.

#### **3.1.2 Reference Start Date and Study Day**

Study Day will be calculated from the reference start date, and will be used to show start/ stop day of assessments and events.

Reference start date is defined as the day of the first administration of trial medication, (Day 1 is the day of the first injection of trial medication), or for subjects randomized but not treated it is the day of randomization, and will appear in every listing where an assessment date or event date appears.

If the date of the event is on or after the reference date then:

- Study Day = (date of event – reference date) + 1.

If the date of the event is prior to the reference date then:

- Study Day = (date of event – reference date).

If the event date is partial or missing, the date will appear partial or missing in the listings, and Study Day, and any corresponding durations will be calculated based on the available level of data. For instance, if day part of one calculation element is unknown, then the calculation will be carried out on month level (using the conversion of 30.4375 days/month).

### **3.1.3 Retests, Unscheduled Visits, Early Termination Data and Rescue Visit**

In the case of a retest, a visit-specific unscheduled assessment will be created. The latest available measurement within the protocol specified +/- 7 days visit window will be used for by-visit summaries.

Unscheduled measurements (unless assigned to a planned visit number as described in the paragraph above) will not be included in by-visit table summaries and by-visit graphs, but will contribute to the last observation carried forward (LOCF) values described in SAP Section 3.1.4 and also contribute to baseline selection as described in Section 3.1.1.

Subjects who prematurely discontinue the study treatment will complete the same assessments as Visit 7 (End of Treatment Visit), and will not be further followed. Early termination data will be summarized and presented together with End of Treatment (EoT) Visit.

Randomized subjects with a central laboratory Fasting Blood Glucose (FBG) and HbA1c value meeting the criteria for lack of glycaemic control during treatment period may be eligible to receive open-label, prescribed rescue medication which may allow the subject to remain in the trial. Randomized subjects who meet the repeated rescue criteria should be scheduled for a rescue visit. Similar to unscheduled measurements, rescue visit results will not be included in by-visit table summaries but will contribute to LOCF algorithm.

Listings will include all scheduled, unscheduled, rescue visit, retest and early discontinuation data collected in the CRF without any unscheduled visit window mapping to scheduled visits.

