4.5 Lack of Glycaemic Control, Rescue Therapy

The subjects will receive investigational product during the entire randomized study period. All subjects will also continue to be provided with open-label 1000 mg metformin tablets with instructions to continue open-label metformin treatment for the duration of the study.

Randomized subjects with a central laboratory FBG and HbA1c value meeting the criteria for lack of glycaemic control during treatment period may be eligible to receive open-label, prescribed rescue medication which may allow the subject to remain in the trial. In case of subjects who are taking glimepiride, increase of dose to 2mg should be preceded first for glycaemic control. If there is lack of glycaemic control with meeting the rescue criteria though increase of dose to 2mg, rescue medication should be prescribed.

Rescue therapy is open-label, any marketed sitagliptinin the dosage approved in Korea. Rescue medication should only be prescribed by investigator if required. No other rescue therapy is allowed. Treatment should be according local standards of care and approved prescribing guidance. All rescue decisions will be based on central laboratory fasting plasma glucose (FBG) and HbA1C.

Subjects who meet the following rescue criteria will be considered for rescue medication.

- Week 4 – 8 (excluding week 8) FBG >13.2 mmol/L (240 mg/dL)
- Week 8 – 24 (including week 24) FBG >11.1 mmol/L (200 mg/dL)
- Week 24 – Week 52 (including Week 52) HbA1c >8.0%

Randomized subjects who meet the repeated rescue criteria should be scheduled for a rescue visit. The rescue visit should take place as soon as possible but not later than 4 weeks after confirmation of repeated FBG and HbA1C. Rescue medication will be dispensed during rescue visit.

On rescue visit, following procedures will be conducted;

Physical exam contains measurement of weight, waist circumflex, pulse and blood pressure. BMI calculation will be conducted.

Subjects will be followed for laboratory assessment of efficacy and safety according to study plan FBG, HbA1c, CBC, AST, ALT, total bilirubin, BUN, creatinine, electrolytes, total cholesterol, triglyceride, HDL-cholesterol, urinalysis, hsCRP, adiponectin. All laboratory assessment will be done in central laboratory.

Diet and life-style counselling will be given to the subject.

Concomitant medications will be checked.

Subject diary will be reviewed for hypoglycaemic events.

New diary will be dispensed to the subjects.

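### The latest-in-window rule of SAP 3.1.3 lets a confirmatory repeat replace a high FBS or HbA1c value but not a low one: a small, conditional downward bias at intermediate visits

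*SAP*

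**What the plan says.** SAP 3.1.3 covers repeats in two steps. First, "In the case of a retest, a visit-specific unscheduled assessment will be created". Then, "The latest available measurement within the protocol specified +/- 7 days visit window will be used for by-visit summaries". No reason for a retest is named, and the earlier value need not be invalid to be displaced. The same section keeps rescue-visit data apart: "rescue visit results will not be included in by-visit table summaries but will contribute to LOCF algorithm".

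Protocol 4.5 is where a result prompts a glycaemic repeat. "Randomized subjects who meet the repeated rescue criteria should be scheduled for a rescue visit", and that visit is due "not later than 4 weeks after confirmation of repeated FBG and HbA1C". All the criteria are high values from the central laboratory:

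- FBG above 240 mg/dL from Week 4 to before Week 8
- FBG above 200 mg/dL from Week 8 through Week 24
- HbA1c above 8.0% from Week 24 through Week 52

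Neither document describes a central-laboratory repeat prompted by a low value, and neither says how soon the confirmatory repeat is drawn.

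SAP 3.8.2 fits the MMRM to all non-missing visit data. It does not say which of two values in one window is used.

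**The concern.** A measured value above a cut-off is, on average, above the person's true level, because values with positive error are over-represented there. If those values alone are re-measured and the new value takes their place, the positive errors are averaged away while the negative errors at the other end stay in the data. This is regression to the mean acting in one direction, and it lowers the visit mean.

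If the two arms have different shares of values above the threshold, the worse-controlled arm is lowered more and a real difference shrinks. At stake are the FBS and HbA1c by-visit summaries and, if the same record feeds the model, the MMRM estimates at those visits.

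**Working it through.** The plan gives no figure on this point, and the sample-size sections are redacted, so there is nothing to reproduce. The check has two parts.

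**Reach.** Set the Protocol 4.5 criteria against the visit schedule.

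| Visit | FBG criterion | HbA1c criterion |
|---|---|---|
| Week 4 | >240 mg/dL | none |
| Week 12 | >200 mg/dL | none |
| Week 24 | >200 mg/dL | >8.0% |
| Week 36 | none | >8.0% |
| Week 52 | none | >8.0%, but SAP 1.2 ends follow-up at this visit |

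**Size.** Let the observed value have mean μ and SD s, with within-person SD w, and let c be the threshold. Let q be the share of repeats that fall in the window. If an independent repeat replaces every value above c, the visit mean shifts by

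Δ = −(w²/s) × φ((c − μ)/s) × q,

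where φ is the standard normal density. The thresholds and the 60 subjects per arm (120 randomized 1:1) come from the documents. μ, s, w and q are assumptions, and q = 1 unless stated.

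*FBS, μ 130 to 150, s 35 to 45, w 10 to 20 mg/dL, c = 200:*
- Smallest (130, 35, 10): (100/35) × φ(2.00) = 2.857 × 0.0540 = 0.15 mg/dL.
- Largest (150, 45, 20): (400/45) × φ(1.11) = 8.889 × 0.2152 = 1.91 mg/dL.
- With c = 240, as at Week 4, the same grid gives 0.01 to 0.5 mg/dL.

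*FBS, less favourable case: between-person SD 30, w 15 to 25, so s = √(900 + w²) = 33.5 to 39.1:*
- Mean 140, c = 200: 0.5 to 2.0 mg/dL.
- Mean 170, c = 200: 1.8 to 4.8 mg/dL. At w = 25 this is (625/39.05) × φ(0.768) = 16.0 × 0.297 = 4.75.

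*HbA1c, μ 7.0 to 7.6, s 0.8 to 1.0, w 0.1 to 0.3, c = 8.0:*
- Smallest (7.0, 0.8, 0.1): 0.0125 × φ(1.25) = 0.0125 × 0.1826 = 0.002 points.
- Largest (7.6, 0.8, 0.3): 0.1125 × φ(0.50) = 0.1125 × 0.3521 = 0.040 points.

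**What reaches the treatment difference.** Only the gap between the two arms' shifts matters. The yardstick is an unadjusted standard error, s × √(2/60).

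| Assumed arm means | Loss of difference | Standard error |
|---|---|---|
| FBS 130 v 150, c = 200 | 0.2 to 1.0 mg/dL | 6.4 to 8.2 |
| FBS 140 v 170, c = 200 | 1.3 to 2.8 mg/dL | 6.1 to 7.1 |
| FBS 140 v 170, c = 240 | 0.3 to 1.0 mg/dL | 6.1 to 7.1 |
| HbA1c 0.3 points apart | 0.001 to 0.010 points | 0.15 to 0.18 |

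For example, at s = 35 and w = 20 the shifts are 1.64 (mean 150) and 0.62 (mean 130), so 1.64 − 0.62 = 1.0 mg/dL is lost.

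**Simulation check** with 2,000,000 subjects. For FBS with mean 140, SD 40 and w 15, the latest-value rule gave −0.71 mg/dL against the true mean, and the formula gives −(225/40) × φ(1.5) = −0.73. Keeping the scheduled value gave +0.02, which is simulation error. Averaging the two values left −0.34, so it only halves the bias. The proportion with HbA1c below 7.0% hardly moved: 36.946% against 36.947%, and at most 27.46% against 27.52%.

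**Partial capture.** If visit days are spread evenly over the 15 days of the window, a repeat 7 days later falls inside it in 8/15 = 53% of cases, and one 14 days later in 1/15 = 7%. Every figure above scales down by that q.

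**The case against.** The strongest reply is that the effect is not in the text. The SAP rule covers retests of any assessment for any reason. The protocol gives no interval for the glucose repeat, and its 4-week limit concerns the rescue visit after confirmation. This stands. A reader might infer that every high value is redrawn and overwritten by rule, but the documents do not say so, and the bias depends on how many repeats fall in the window.

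Second, a reader might infer that the Week 52 comparison is biased. For FBS that is not supported, because no FBG criterion applies after Week 24. For HbA1c the criterion includes Week 52, but follow-up ends there, so a repeat is unlikely.

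Third, the rule is worded for by-visit summaries, and carry-over into the MMRM is not stated. That is fair. It is still the natural reading: SAP 3.1.3 describes in-window unscheduled values as assigned to a planned visit, the SAP 3.8.2 code selects on visit number with an unstructured covariance over visits, and no other post-baseline rule chooses between two in-window values.

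Fourth, the latest-value rule does useful work. Protocol 3.8 has the whole visit rescheduled when the fasting or dosing instructions were not followed, and the later sample is then the better one. This stands, and the fix has to preserve it.

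Finally, a reader might suspect a further imbalance if glimepiride is raised between test and repeat, since Protocol 4.5 puts that step before rescue. The timing is not stated and this was not modelled, so nothing is claimed from it.

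**Conclusion.** The concern holds in a limited form. The selection rule is one-sided for glycaemic repeats prompted by their own result. Where those repeats fall inside the window, it lowers mean FBS at Weeks 4, 12 and 24 and mean HbA1c at Weeks 24 and 36.

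The per-arm shift at the 200 mg/dL threshold is about 0.2 to 2 mg/dL at means of 130 to 150 and up to about 5 at a mean of 170. It is smaller at the 240 threshold of Week 4, and at most about 0.04 points for HbA1c. The loss in the treatment difference is towards zero and stays below half an unadjusted standard error even in the least favourable case (2.8 against 7.1 mg/dL). These sizes rest on assumed means and SDs and on full capture, so they are upper values for those assumptions.

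The affected endpoints are secondary, and SAP 3.1.6 has them interpreted descriptively. The documents do not support reading this as a threat to the primary DXA result, to Week 36 or 52 FBS, or to the glycaemic responder rate. Severity: minor.

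**What to change.** In SAP 3.1.3, state for both the by-visit summaries and the MMRM:

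- The scheduled-visit sample is the value used.
- An in-window repeat replaces it only if the scheduled sample is missing, invalid, or taken without following the Protocol 3.8 visit instructions. In the last case the rescheduled visit counts as the scheduled visit.
- Confirmatory repeats prompted by the result itself appear in listings and serve rescue decisions only.

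Add a cross-reference in SAP 3.8.2 so that the model and the tables use the same record. Limiting replacement to samples that the laboratory declares invalid would be too narrow, because a laboratory cannot be expected to recognise a non-fasted sample. Averaging the two values is not a substitute, since it removes only half the bias.

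The cost is a few lines of SAP text and a record-selection flag in programming. No new data are needed, and no clinical rule changes.

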### **3.1.4 Missing Data**

LOCF will be used for imputation of missing values of glycaemic control status (HbA1c <7.0%).

Last observation will be carried forward as many times as needed. All available data, including unscheduled visits and rescue visits, will be taken into account when identifying the last observation to be carried forward.

### **3.1.5 Multicenter Study**

Study will include data from approximately 17 sites in Korea, all data will be pooled before analysis.

### **3.1.6 Multiple Comparisons/ Multiplicity**

The statistical significance levels will not be adjusted for multiple hypothesis testing. Consequently, all statistical tests performed with secondary/sensitivity analysis will be interpreted only descriptively.

## **3.2 Disposition and withdrawals**

All subjects who provide informed consent will be accounted for in this study.

The following subject disposition and withdrawal events will be presented for the ENR set:

- Informed consent signed (ENR)
- Screen failures
- Passed screening but not randomized
- Randomized (RND)
- Randomized but not treated
- Treated, Safety Analysis Set (SAF)
- Full Analysis Set (FAS)
- Per Protocol Analysis Set (PPS)
- Prematurely discontinued from treatment/study
  - Primary reason for premature discontinuation
- Completed treatment/study.

Subjects violating each inclusion and exclusion criteria will only be listed for the ENR set.

## **3.3 Demographics and Other Baseline Characteristics**

No statistical testing will be carried out for demographic or other baseline characteristics.

The following demographic characteristics will be presented for SAF:

- Age (years) - Calculated relative to date of ICF
- Gender
  - Male
  - Female

- Post-menopausal
- Non-menopausal
  - Pregnancy test positive
  - Pregnancy test negative
  - Pregnancy test not performed
- Ethnicity
  - Korean
  - Other
- Subject Experienced Type 1 Diabetes
  - Active
  - Cured
- Time since Type 2 Diabetes diagnosis (years) - Calculated relative to date of ICF

The following baseline characteristics will be presented for FAS:

- Baseline total body fat mass (g)
- Baseline total body lean mass (g)
- Baseline total body fat percentage (%)
- Baseline HbA1c level (%)
- Baseline fasting blood glucose level (mg/dL)
- Baseline body weight (kg)
- Baseline waist circumference (cm)
- Baseline BMI (kg/m^2)
- Baseline SBP (mmHg)
- Baseline DBP (mmHg)
- Baseline VAT/SAT ratio
- VAT and SAT area
- Baseline hsCRP (mg/L)
- Baseline Adiponectin (ng/mL)

Definition of baseline is discussed in SAP Section 3.1.1.

### 3.3.1 Derivations

- Age (Years) will be calculated relative to the date of informed consent:

- Age (Years) = (Date of Informed Consent Signed – Date of Birth + 1)/365.25
- Time since Type 2 Diabetes diagnosis (years) = (Date of Informed Consent Signed – Date of first diagnosis of Type 2 Diabetes + 1)/365.25
- BMI (kg/m^2) = Weight (kg)/ Height (m^2)

### 3.4 Surgical History, Medical History and Concomitant Procedures

Surgical and medical history will be collected on CRF page “pMH” whilst concomitant procedures will be collected on CRF page “pCP”. Captured data will be presented for SAF population.

Collected records will be coded using MedDRA version 20.0 or higher. All coded terms will be summarized by SOC and PT. Subject having multiple records in one category will be counted only once. Records will be presented in alphabetical order.

Additionally, for concomitant procedures, reasons for procedure will be summarized and rescue procedures will be presented additionally.

### 3.5 Medications

Medications will be captured on CRF page “pCM”.

“Prior” medications are medications which stopped prior to the first dose of study medication. All other medications will be considered concomitant. In the case where it is not possible to define a medication as prior or concomitant, the medication will be classified by the worst case; concomitant.

All concomitant medications, including rescue medications, will be summarized for SAF set.

All concomitant medications will be coded using AZ Drug Dictionary (AZDD) Version 15.2 to identify their Anatomical Therapeutic Chemical (ATC) classification code and generic term. Multiple drug usage by a patient will be counted only once for each therapeutic class. Records will be presented in alphabetical order.

Rescue medication will be summarized additionally.

### 3.6.1 Derivations

- Actual duration of exposure (days) = stop date of administration – start date of administration +1

- Duration of interruptions (days) = Sum of (stop date of each interruption – start date of each interruption +1)
  - For Metformin, if Metformin consumption stops before study medication, duration between Metformin termination and end of study treatment will be considered Metformin interruption.

- Actual dose intensity (mg/day) = Cumulative dose (mg) / Actual duration of exposure (days)

- Total planned dose (mg) of subjects receiving Glimepiride =  $\sum_{all\ i} (\text{prescribed dose level at period } i) \times (\text{stop date of period } i - \text{start date of period } i)$ ,

Where each period refers to a time frame whose prescribed dose level is constant. Whenever the prescribed dose level is changed, a new period shall be created.

- Total Planned dose (mg) of subjects receiving Dapagliflozin = 10 mg/day × Actual duration of exposure (day).
- Compliance is based cumulative dose and the total planned dose, and will be calculated as follows:

$$\text{Compliance (\%)} = 100\% \times \frac{\text{Cumulative Dose}}{\text{Total Planned Dose}}$$

- Compliance will be further categorized into 3 levels:
  - <80%
  - ≥80% and ≤120%
  - >120%

### 3.7 Primary Efficacy Analysis

#### 3.7.1 Primary Efficacy Variable

The primary efficacy variable of the study is the change in total body fat mass (in grams and percentages) from baseline using DXA scan in 52 weeks after the start of the treatment, which is defined as the total body fat mass at Week 52 subtracts total body fat mass at baseline.

Total body fat mass and percentages will be captured on CRF page “pDXA1” and “pDXA”.

#### 3.7.2 Primary Analysis of Primary Endpoint

The test for equivalence between two treatment groups will be performed for FAS population.

The hypothesis to be tested are given as:

$$H_0: \mu_T = \mu_C \text{ Versus } H_A: \mu_T \neq \mu_C$$

Where  $\mu_T$  denotes the mean change in test results from Baseline to Week 52 of subjects who received Dapagliflozin (Treatment under investigation, T) and  $\mu_C$  denotes the mean change in test results from Baseline to Week 52 of subjects who received Glimepiride (Comparator, C).

The primary efficacy variable will be analysed using an ANCOVA model with treatment group as factor and Baseline test results as a covariate, as following:

$$E(Y_{ij}) = \mu_{..} + Trt_i + BaselineY_{ij}$$

Where  $i=1, 2; j=1, 2, \dots, n_i$ .

$E(Y_{ij})$  denotes the mean change in total body fat mass (in g)/percentages from baseline to week 52 of  $j^{\text{th}}$  subject in treatment group  $i$ .

$\mu_{..}$  denotes the overall mean total body mass from baseline to week 52.

$Trt_i$  denotes the treatment effect of each group from the overall mean.

$BaselineY_{ij}$  denotes the baseline total body fat mass of  $j^{\text{th}}$  subject in treatment group  $i$ .

The model will be used to derive a least squares estimate of the treatment difference with corresponding two-sided 95% confidence interval (CI) and two-sided Wald p-value.

Further, two-sided 95% CIs for the primary endpoint within each treatment group will be calculated. Model diagnosis statistics will be presented.

Following SAS code can be used to obtain above statistics:

```
proc glm data=DD;  
class TRTP;  
model ChgFat=TRTP BaseFat /solution;  
lsmeans TRTP/Pdiff=CONTROL('Comparator') cl;  
run; quit;
```

In order to descriptively present the primary endpoint, total body fat mass in grams and total percent of body fat from baseline and Week 52 will be presented for FAS set and listed for SAF set. Change from baseline to Week 52 for FAS subjects will also be summarized.

### 3.7.3 Sensitivity Analysis of Primary Endpoint

To evaluate the impact of protocol compliance on primary efficacy endpoint, primary efficacy analysis method will be repeated on the PPS population.

To evaluate the impact of base-weight in total body fat mass, primary efficacy analysis will be repeated based on total body fat percentage (%) for both FAS and PPS.

To evaluate the impact of gender ratio on primary efficacy endpoint, primary efficacy analysis method will be performed using ANCOVA model with treatment group as factor and Baseline test results and gender as a covariate on FAS and PP population, as following.

$$E(Y_{ij}) = \mu_{..} + Trt_i + BaselineY_{ij} + GenderZ_{ij}$$

Where  $i=1, 2; j=1, 2, \dots, n_i$ .

$E(Y_{ij})$  denotes the mean change in total body fat mass (in g or %) from baseline to week 52 of  $j^{\text{th}}$  subject in treatment group  $i$ .

$\mu_{..}$  denotes the overall mean total body mass (in g or %) from baseline to week 52.

$Trt_i$  denotes the treatment effect of each group from the overall mean.

$BaselineY_{ij}$  denotes the baseline total body fat mass of  $j^{th}$  subject in treatment group  $i$ .

$GenderZ_{ij}$  denotes the gender of  $j^{th}$  subject in treatment group  $i$ .

The model will be used to derive a least squares estimate of the treatment difference with corresponding two-sided 95% confidence interval (CI) and two-sided Wald p-value.

Further, two-sided 95% CIs for the primary endpoint within each treatment group will be calculated. Model diagnosis statistics will be presented.

Following SAS code can be used to obtain above statistics:

```
proc glm data=DD;  
class TRTP gender;  
model ChgFat=TRTP BaseFat gender/solution;  
lsmeans TRTP/Pdiff=CONTROL('Comparator') cl;  
run; quit;
```

